3.3 Safety Variables

The safety variables include the following:

- Slit Lamp Biomicroscopy
- Pin-hole Visual Acuity
- Intraocular Pressure
- Dilated Indirect Ophthalmoscopic Examination
- Adverse Events

Statistical Analysis Plan Protocol RTA 408-C-1307

307 1.0

Version

4. Statistical Hypotheses

The null and alternative hypotheses are as follows:

- H_{011} : The difference, between study eyes treated with the 1.0% concentration of RTA 408 Ophthalmic Suspension and study eyes treated with placebo, in the proportion of study eyes with absence of anterior chamber cells (score of 0) at Visit 5 (Day 15) = 0.
- H_{A11}: The difference, between study eyes treated with the 1.0% concentration of RTA 408 Ophthalmic Suspension and study eyes treated with placebo in the proportion of study eyes with absence of anterior chamber cells (score of 0) at Visit 5 (Day 1\$)0, with superiority claimed if the difference is greater than 0 (RTA 408 Ophthalmic Suspension Placebo).
- H₀₁₂: The difference, between study eyes treated with the 0.5% concentration of RTA 408 Ophthalmic Suspension and study eyes treated with Placebo, in the proportion of study eyes with absence of anterior chamber cells (score of 0) at Visit 5 (Day 15) = 0.
- H_{A12}: The difference, between study eyes treated with the 0.5% concentration of RTA 408 Ophthalmic Suspension and study eyes treated with placebo in the proportion of study eyes with absence of anterior chamber cells (score of 0) at Visit 5 (Day 1\$)0, with superiority claimed if the difference is greater than 0 (RTA 408 Ophthalmic Suspension Placebo).

and

- H_{021} : The difference, between study eyes treated with the 1.0% concentration of RTA 408 Ophthalmic Suspension and study eyes treated with placebo in the proportion of study eyes with absence of pain (score of 0) at Visit 3 (Day 4) = 0.
- H_{A21}: The difference, between study eyes treated with the 1.0% concentration of RTA 408 Ophthalmic Suspension and study eyes treated with placebo in the proportion of study eyes with absence of pain (score of 0) at Visit 3 (Day 4)≠ 0, with superiority claimed if the difference is greater than 0 (RTA 408 Ophthalmic Suspension Placebo).
- H_{022} : The difference, between study eyes treated with the 0.5% concentration of RTA 408 Ophthalmic Suspension and study eyes treated with placebo in the proportion of study eyes with absence of pain (score of 0) at Visit 3 (Day 4) = 0.
- H_{A22}: The difference, between study eyes treated with the 0.5% concentration of RTA 408 Ophthalmic Suspension and study eyes treated with placebo in the proportion of study eyes with absence of pain (score of 0) at Visit 3 (Day 4)≠ 0, with superiority claimed if the difference is greater than 0 (RTA 408 Ophthalmic Suspension Placebo).

5. Sample Size and Power Considerations

Statistical Analysis Plan Protocol RTA 408-C-1307

SIGNIFICANTLY DIFFERENT

Version 1.0

The primary analyses will first test the difference in the proportion of patients with absence of anterior chamber cells in the study eye between the 1.0% concentration of RTA 408 Ophthalmic Suspension and placebo and between the 0.5% concentration of RTA 408 Ophthalmic Suspension and placebo at Visit 5 (Day 15) using the Pearson chi-squared statistic at a 1-sided alpha=0.10.

If the proportion of patients with a grade of '0' for anterior chamber cells is statistically significantly higher for the 1.0% concentration versus placebo at a 1-sided alpha=0.10, then the hierarchical hypothesis testing will compare the proportion of patients with absence of ocular pain at Visit 3 (Day 4) between the 1.0% concentration of RTA 408 Ophthalmic Suspension and placebo using the Pearson chi-squared statistic at a 1-sided alpha=0.10.

If the proportion of patients with a grade of '0' for anterior chamber cells is statistically significantly higher for the 0.5% concentration versus placebo at a 1-sided alpha=0.10, then the hierarchical hypothesis will compare the proportion of patients with absence of ocular pain at Visit 3 (Day 4) between the 0.5% concentration of RTA 408 Ophthalmic Suspension and placebo using the Pearson chi-squared statistic at a one-sided alpha=0.10.

If the test of the difference in the proportion of study eyes with absence of anterior chamber cells is statistically significant in favor of the 1.0% or 0.5% concentration of RTA 408 Ophthalmic Suspension versus placebo, then the study will be considered a success and the concentration(s) of RTA 408 Ophthalmic Suspension showing statistical significance will be declared to be superior to placebo in the proportion of study eyes with absence of anterior chamber cells at Visit 5 (Day 15).

6. General Statistical Consider	rations			
All data analysis will be performe	d by	ter the study is completed		
and the database has been locked and released for un-masking. Statistical programming and				
analyses will be performed using	SAS® Version 9.2 or higher. Outp	out will be provided in RTF format		
for tables and PDF format for tab	les, listings, and figures. All study	data will be listed by patient,		
treatment, and visit (as applicable	∍).			
13/FEB/2014	Confidential	Page 7 of 21		

Statistical Analysis Plan Protocol RTA 408-C-1307

Version

1.0

SIGNIFICANTLY DIFFEREN

Continuous and ordinal variables will be summarized using descriptive statistics (i.e., number of observations (n), arithmetic mean, standard deviation (SD), minimum, median, and maximum). Categorical variables will be summarized descriptively using counts and percentages. Means and medians will be rounded to one decimal more than the collected data; SDs will be rounded to two decimal place more than the collected data. All percentages will be rounded to one decimal place

Unless otherwise specified, summaries will be presented by treatment group and visit. The baseline measure is defined as the last non-missing measure prior to initiation of investigational treatment, which is Visit 2 (Day 1) for all measures with the exception of the dilated indirect ophthalmoscopic examination where the Visit 1 (\geq 28 days prior to surgery) will serve as baseline. Differences between active treatment groups and placebo will be calculated as Active minus Placebo. Changes from baseline will be calculated as follow-up value minus baseline value. All statistical tests will be one-sided with a significance level of 0.10 (α = 0.10). Confidence intervals (CI) for differences between treatment groups will be two-sided at 80% confidence as well as 95% confidence. All p values will be rounded to four decimal places; p values less than 0.0001 will be presented as "< 0.0001"; p values greater than 0.9999 will be presented as ">0.9999".

All study data will be listed by patient, treatment, and visit (as applicable), based on all enrolled patients.

6.1 Unit of Analysis

(i.e., XX.X%).

The unit of analysis in this study will be the study eye for all efficacy and safety summaries.

Additionally, non-ocular AEs will be presented at the patient level. Non-study eye safety summaries will also be presented as appropriate.

6.2 Adjustments for Multiplicity

To address the two primary efficacy variables employed in this study, the primary efficacy variables have been prioritized into a hierarchical structure. In order to test ocular pain for RTA Ophthalmic Suspension 1.0%, anterior chamber cells must have shown statistically significant improvements for RTA Ophthalmic Suspension 1.0% versus placebo using a one-sided significance level of 0.10. This same strategy is applicable to the 0.5% concentration of RTA Ophthalmic Suspension.

No multiplicity adjustments will be employed for the multiplicity of tests due to two concentrations of active.

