6 STUDY PARAMETERS

6.1 Efficacy Measures

The hierarchical primary efficacy variables are the following:

- 1. Absence of anterior chamber cells (i.e., score of '0') at Visit 5 (Day 15) for:
 - a. The 1.0% concentration of RTA 408 Ophthalmic Suspension compared to Placebo
 - b. The 0.5% concentration of RTA 408 Ophthalmic Suspension compared to Placebo.
- 2. Absence of pain (i.e., score of '0') at Visit 3 (Day 4) for:
 - a. The 1.0% concentration of RTA 408 Ophthalmic Suspension compared to Placebo; to be tested if 1a. is statistically significant in favor of the active arm.
 - b. The 0.5% concentration of RTA 408 Ophthalmic Suspension compared to Placebo; to be tested if 1b. is statistically significant in favor of the active arm.
 - 6.1.1 Secondary Efficacy Variables
 - 1. Absence of anterior chamber cells at Visits 3, 4, or 6 (Days 4±1, 8±1, or 21±1, respectively)
 - 2. Absence of pain at Visits 4, 5 or 6 (Days 8 ± 1 , 15+1 or 21 ± 1 , respectively)
 - 3. Absence of flare at Visits 3, 4, 5 or 6 (Days 4 ± 1 , 8 ± 1 , 15 ± 1 or 21 ± 1 , respectively)

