10.10 Primary Efficacy Analyses

The primary efficacy variables, study eyes with absence of anterior chamber cells at Visit 5 (Day 15) and study eyes with absence of pain at Visit 3 (Day 4), will be summarized using discrete summary statistics, including 90% asymptotic normal confidence intervals for each treatment group. The primary efficacy analyses will first test the difference in proportion of study eyes with a grade of '0' in anterior chamber cells between the 1.0% concentration of RTA 408 Ophthalmic Suspension and placebo and between the 0.5% concentration of RTA 408 Ophthalmic Suspension and placebo at Visit 5 (Day 15) using the Pearson chi-squared statistic.

If the proportion of patients with a grade of '0' for anterior chamber cells is statistically significantly higher for the 1.0% concentration versus placebo at a 1-sided alpha=0.10, then the hierarchical hypothesis testing will compare the proportion of patients with absence of ocular pain at Visit 3 (Day 4) between the 1.0% concentration of RTA 408 Ophthalmic Suspension and placebo using the Pearson chi-squared statistic at a 1-sided alpha=0.10.

If the proportion of patients with a grade of '0' for anterior chamber cells is statistically significantly higher for the 0.5% concentration versus placebo at a 1-sided alpha=0.10, then the hierarchical hypothesis will compare the proportion of patients with absence of ocular pain at Visit 3 (Day 4) between the 0.5% concentration of RTA 408 Ophthalmic Suspension and placebo using the Pearson chi-squared statistic at a one-sided alpha=0.10.

Additionally, 95% confidence intervals will be constructed around the difference in proportions for each primary outcome using asymptotic normal approximations. Fisher's exact tests will be employed in cases of expected counts less than five.

If the test of the difference in the proportion of study eyes with absence of anterior chamber cells is statistically significant in favor of the 1.0% or 0.5% concentration of RTA 408 Ophthalmic Suspension versus placebo, then the study will be considered a success and the concentration(s) of RTA 408 Ophthalmic Suspension showing statistical significance will be declared to be superior to placebo in the proportion of study eyes with absence of anterior chamber cells at Visit 5 (Day 15).

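### Does testing two doses at an unadjusted one-sided 0.10, with success on either, call for a multiplicity correction?

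*SAP*

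**What the plan says.** SAP section 6 sets the level for every test: "All statistical tests will be one-sided with a significance level of 0.10". SAP section 5 applies it to the first primary variable, comparing each concentration with placebo on absence of anterior chamber cells at Visit 5 "using the Pearson chi-squared statistic at a 1-sided alpha=0.10". The success rule in the same section is met by a significant result "in favor of the 1.0% or 0.5% concentration of RTA 408 Ophthalmic Suspension versus placebo, then the study will be considered a success". Protocol sections 10.6 and 10.10 carry the same rule, and the winning concentration or concentrations are then declared superior on that endpoint.

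Protocol section 6.1 introduces the endpoints with "The hierarchical primary efficacy variables are the following". The gates that follow run within a dose: pain at Day 4 is tested for 1.0% only if cells are significant for 1.0%, and likewise for 0.5%. SAP section 6.2 describes the gate for 1.0% and adds "This same strategy is applicable to the 0.5% concentration of RTA Ophthalmic Suspension". On the two doses it says: "No multiplicity adjustments will be employed for the multiplicity of tests due to two concentrations of active".

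Neither document gives a study-wise or family-wise error rate.

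**The concern.** The word hierarchical and the listing 1a, 1b, 2a, 2b can be read as one controlled sequence. It is not one. There are two parallel chains, one per dose, and the success rule needs only one of the two cell tests to pass. The cells-to-pain gate gives that rule no protection, because success rests on cells alone.

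With two chances to win, the rule fires more often than 10% of the time when the drug is inert. The only error level printed is 0.10, so a reader could take it for the error rate of the success declaration. The decision to continue development and the word superior both rest on that declaration, and 0.10 one-sided is already lenient. The same inflation can reach pain: if both doses truly clear cells but neither affects pain, two ungated pain tests are run at 0.10 each.

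**Working it through.** **Inputs from the documents.** Level 0.10, one-sided, per test (SAP 5 and 6). Allocation 1:1:1 with one placebo arm (Protocol 8.1.5). Enrolled 35 per arm, with 31 per arm to complete (Protocol 5.1). Pearson chi-squared, with Fisher's exact test when an expected count is below five (Protocol 10.10, SAP 14.1). No interim analysis.

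**Assumed inputs.** Clearance rates. The available text gives none, so ranges are shown.

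**1. The plan's own figure.** One-sided 0.10 corresponds to a critical z of 1.2816. Each test has size 0.10 by construction (simulated: 0.0999). The stated level is correct for what it describes.

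**2. Either-dose error, normal approximation.** With equal arms, Z1 = (X1 − X0)/√2 and Z2 = (X2 − X0)/√2. The shared X0 gives a correlation of 1/2. When neither dose works:

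P(at least one win) = 1 − Φ2(1.2816, 1.2816; ρ = 0.5) = 0.1676.

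Four million simulated trials also gave 0.1676, with both tests significant in 0.0323. As a check, 0.10 + 0.10 − 0.0323 = 0.1677. Independent tests would give 1 − 0.9² = 0.19, and the Bonferroni bound is 0.20.

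**3. Either-dose error, exact.** Let b(x) be the binomial probability of x clearances on placebo and q(x) the chance that one active arm beats that x under the Pearson/Fisher rule. The error is 1 − Σ b(x)[1 − q(x)]².

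| Assumed common clearance | 35 per arm | 31 per arm |
|---|---|---|
| 5% | 4.9% | 3.9% |
| 10% | 11.0% | 10.0% |
| 15% | 14.4% | 15.0% |
| 20% | 16.0% | 17.2% |
| 30% | 16.7% | 17.9% |
| 50% | 15.9% | 15.0% |
| 70% | 17.4% | 17.9% |
| 85% | 14.1% | 13.9% |

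At low rates the Fisher fallback is conservative and pulls the error down.

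**4. When one dose works.** Only the other cell test can then give a false cell claim, and that test is run at 0.10, so the rate is about 10%. The 17% belongs to the case where neither dose works.

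**5. What 10% control would cost.** The Dunnett cut-off solves 1 − Φ2(c, c; 0.5) = 0.10, giving c = 1.577, or nominal p = 0.0574 per dose. Under an assumed 20% on placebo and 45% on both doses (exact calculation):

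| | Per-dose power, 0.10 → 0.0574 | Either-dose power, 0.10 → 0.0574 |
|---|---|---|
| 35 per arm | 84% → 76% | 93% → 88% |
| 31 per arm | 82% → 72% | 92.8% → 85.9% |

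A fixed sequence 1a, 1b, 2a, 2b at 0.10 per step also holds 10%. But the 1.0% pain test could then be reached only if the 0.5% cell test had passed too. At 35 per arm, with 20% on placebo and 45% on 1.0%, the chance of reaching that pain test falls from 84% under the plan to:

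- 75% if the 0.5% rate is also 45%
- 52% if it is 35%
- 37% if it is 30%

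**The case for a change.** The strongest case for acting is that disclosing the absence of an adjustment is not the same as disclosing its effect. The plan is more than exploratory: it fixes a yes/no success criterion in advance and attaches a superiority declaration to it. A team that acts on that declaration should know it would come up about one time in six with an inert drug. Adding a sentence with that rate, and Dunnett-adjusted p-values beside the unadjusted ones, would cost no power and alter no test.

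The arithmetic in that case stands, and so does the observation that the study-wise rate is not printed. What does not stand is the idea that something stated is wrong. Each mention of 0.10 in these sections is as the level of a test, SAP 6.2 deals with the two concentrations directly, and the either-dose rule is set out in full in both documents. A statistician can work out the 17% from those facts. Printing it, or adding supportive p-values, would leave the tests, the success rule and the conclusion as they are. The remedies that would change the error rate are not corrections: each gives up power, or the link between a dose's own cell result and its own pain test.

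**Conclusion.** No change is needed. The either-dose success rule has a false-success rate of 16.8% when neither dose works. That rests on equal arms, a shared placebo group and the normal approximation. The exact figure is about 14% to 18% for assumed clearance of 15% to 85% at 31 or 35 per arm, and about 4% to 11% at 5% to 10%. If one dose works, the false cell claim rate for the other is about 10%. These figures contradict nothing in the protocol or SAP, which state a per-test level and openly decline to adjust across doses.

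For a Phase 2 dose-ranging trial, the first clinical study of this formulation, accepting that rate in return for more power to detect a useful dose is a reasonable screening choice. On the assumed 20% versus 45%, Dunnett control would cost 5 to 7 points of either-dose power and roughly 8 to 10 points per dose, and the strict four-step sequence could block the 1.0% pain claim because of a weak 0.5% result. Those are design preferences for the sponsor. Readers of the results should take 0.10 as the level per comparison.

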6.3 Handling of Dropouts or Missing Data

The primary analyses of all efficacy data will use LOCF to impute missing data; data for visits after a patient is discontinued for lack of efficacy will be imputed as failures for success/failure endpoints and will be imputed using LOCF for other endpoints.

Statistical Analysis Plan Protocol

Version SIGNIFICANTLY D

RTA 408-C-1307 1.0

Per Protocol analyses will use observed data only, with the exception of patients who have missing data due to discontinuation of study treatment for lack of efficacy; for these patients, data after discontinuation will be imputed as failures.

To check robustness of results, sensitivity analyses of the primary efficacy data will be performed. These include analyses of observed data only, imputing data from patient visits after discontinuation for lack of efficacy as failures and analyses in which all missing data are imputed using multiple imputation methodology.

6.4 Unscheduled Visits

Unscheduled data, such as information from unscheduled visits or Investigator comments, will be included in the data listings. In general, these data will be excluded from the summary tables unless otherwise specified.

7. Study Design and Procedures

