8.4.2 Unscheduled Visits

These visits may be performed in order to ensure patient safety. All information gathered at unscheduled visits should be recorded on the Unscheduled Visit pages of the Source Document and corresponding eCRF.

If a randomized patient does not attend their scheduled visit, the eCRF pages for the missed visit will be skipped.

³ These procedures are to be completed on Visit 6 only if not performed at Visit 5.

All efforts should be made to schedule patients for an Exit Visit to complete Exit Procedures. Information from Early Exit Visits should be recorded on the Visit 6/Exit Visit pages.

Evaluations that may be conducted at an Unscheduled Visit (as appropriate, depending on the reason for the visit) include:

- Update Medical/Medication History
- Review/Collect Study Drug Compliance Diary and Study Drug
- Assessment of ocular pain
- Pin-hole visual acuity
- Slit lamp biomicroscopy
- Assessment of Ocular Inflammation
- Intraocular pressure measurement
- Dilated indirect ophthalmoscopic examination
- Assessment of AEs
- Urine pregnancy test (for females of childbearing potential)

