10 STATISTICAL HYPOTHESES AND METHODS OF ANALYSES

10.1 Study Populations

10.1.1 Intent-to-Treat Population

The Intent-to-Treat (ITT) population consists of all patients who are randomized. All data will be included and no patients will be excluded because of protocol violations. The ITT population will be analyzed as randomized and will be used for the efficacy analyses.

10.1.2 Safety Population

The Safety population includes all randomized patients who received at least one dose of investigational treatment. The Safety population will be analyzed as treated and will be used for the safety analyses. No data will be excluded for any reason.

10.1.3 Per Protocol Population

The Per Protocol (PP) population is a subset of the ITT population and includes patients who remain in the study through Visit 5 (Day 15) with no major protocol violations that would affect the assessment of the primary efficacy endpoints of the study. Patients without major protocol violations thought to affect the primary efficacy outcome who discontinue the study due to lack of efficacy will be analyzed in the PP analysis with missing data after discontinuation imputed as failures for success/failure endpoints and will be imputed using last observation carried forward (LOCF) for other endpoints. Otherwise, this population will be analyzed as treated using observed data only for confirmatory analyses.

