9.3 Safety

The Safety population includes all randomized patients who received at least one dose of investigational treatment. The Safety population will be analyzed as treated and will be used for the safety analyses. No data will be excluded for any reason.

10. Patient Disposition

Patient disposition will be presented in terms of the numbers and percentages of patients who were randomized. Patients who are not discontinued from the study will be considered study completers.

The total number of screened subjects with the number and percentage of screen failure subjects and reasons for screen failure will be displayed with the percentages calculated using total number of 13/FEB/2014 Confidential Page 12 of 21

Statistical Analysis Plan Protocol RTA 408-C-1307

Version 1.0

screen failures as the denominator. The number of patients in each of the populations (ITT, PP and Safety) will be displayed by treatment and percentages will be calculated using randomized patients as the denominator.

The number and percentage of patients with major protocol deviations will be summarized by treatment group for all randomized patients. The protocol deviations that will be summarized include: non-compliance with any scheduled study visit, non-compliance with study treatment, use of disallowed concomitant medications, non-compliance with study inclusion or exclusion criteria, non-compliance with study assessment procedures and other. A patient listing will be provided that includes the date of the deviation, the deviation description and the classification of whether the deviation was judged to be major or minor.

The number and percentage of patients prematurely discontinued from study treatment and the reasons for study treatment discontinuation will be summarized by treatment group for all randomized patients. The reasons for study treatment discontinuation that will be summarized include: adverse event (AE), protocol violation, lack of efficacy, administrative reasons, sponsor termination of study, voluntary withdrawal, pregnancy and other. A patient listing will be provided that includes the date of and reason for premature study treatment discontinuation.

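### Safety exam readings from unscheduled visits reach only the listings, and the protocol's any-time IOP ≥30 mm Hg proportion is lost without being declared

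*SAP*

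**What the plan says.** Protocol 8.4.2 gives the purpose of off-schedule visits: "These visits may be performed in order to ensure patient safety". The evaluations that may be done there include pin-hole acuity, slit lamp, "Intraocular pressure measurement" and dilated ophthalmoscopy. The readings are captured: "All information gathered at unscheduled visits should be recorded on the Unscheduled Visit pages of the Source Document and corresponding eCRF".

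SAP 6.4 then sets the reporting rule. On listings: "Unscheduled data, such as information from unscheduled visits or Investigator comments, will be included in the data listings". On tables: "In general, these data will be excluded from the summary tables unless otherwise specified".

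Protocol 10.12 and the synopsis ask for IOP to be summarised at each visit. They also ask for the proportion of patients whose IOP is 30 mm Hg or more at any time once treatment has begun. SAP 15.5 gives the same threshold as a proportion at each visit. SAP 17, which lists departures from the protocol, names only the Per Protocol imputation.

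SAP 9.3 closes its definition of the Safety population with: "The Safety population will be analyzed as treated and will be used for the safety analyses. No data will be excluded for any reason". Protocol 10.1.2 has the same closing sentence.

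**The concern.** Patients are usually examined off-schedule because something has prompted it, so the readings left out of the tables are not a random sample. A pressure rise or acuity loss that arises between scheduled visits, is seen at an extra visit and has gone by the next scheduled one leaves no trace in the exam tables.

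Safety is part of the primary objective, and the synopsis describes this as the first clinical study of the suspension. A reader of the IOP table would take its ≥30 mm Hg row as the answer to the protocol's question of how many patients ever reached that level. Under the SAP, it would not be.

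**Working it through.** **Step 1. Is there an exception to SAP 6.4?** The default exclusion yields only where something else is specified, so I compared each safety exam section with the protocol.

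| Exam | Protocol 10.12 asks for | SAP gives | Exception for unscheduled readings | Where an off-schedule-only finding appears |
|---|---|---|---|---|
| IOP | By-visit summaries, plus ≥30 mm Hg at any time on treatment or after | 15.5: by visit; ≥10 mm Hg rise, and ≥30 mm Hg per visit | None | Listing 16.3.2.1 |
| Slit lamp | Each visit | 15.2: each visit, with shifts from Visit 2 | None | Listing 16.3.2.2 |
| Pin-hole acuity | Each visit, including a 2-line change since the previous visit | 15.4: by visit, 2-line worsening since the previous visit | None | Listing 16.3.2.3 |
| Dilated ophthalmoscopy | Each visit | 15.3: Visits 1 and 6 | None | Listing 16.3.2.4 |

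The table list in SAP 20 has no any-time or worst-value safety table. The default therefore governs all four exams.

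**Step 2. Does this defeat something the protocol requires?** For slit lamp, acuity and ophthalmoscopy the protocol asks only for by-visit summaries, so the SAP is consistent with it. For IOP ≥30 mm Hg it is not. An any-time proportion counts a patient once if any post-dose reading reaches the threshold. A set of per-visit proportions does not give that count, even from scheduled visits alone, because the same patient may appear at several visits. Dropping unscheduled readings removes further patients from the count.

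**Step 3. Could a finding fall between visits?** Nominal scheduled days are 1, 4, 8, 15 and 21. The gaps are 4 − 1 = 3, 8 − 4 = 4, 15 − 8 = 7 and 21 − 15 = 6 days. That leaves room for a transient finding.

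**Step 4. Scale.** The documents state no figure on this point, so there is none to reproduce. Let x be the number of patients in an arm whose only IOP reading of ≥30 mm Hg is off-schedule. With 35 per arm (Protocol 5.1), all assumed dosed, the any-time proportion is understated by x/35:

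- x = 0: no effect
- x = 1: 1/35 = 2.9 percentage points (1/31 = 3.2 on the planned 31 completers)
- x = 2: 2/35 = 5.7 percentage points

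These values of x are assumptions. The documents give no expected number of unscheduled visits.

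**The case against.** The strongest reply is that the main safety analysis is not visit-based. Protocol 10.12 names ocular treatment-emergent adverse events in the study eye as the primary safety analysis, and SAP 15.1 defines such events by when they occur or worsen. An event found at an extra visit and recorded as an adverse event is still tabulated. This stands: a reader might infer that harm seen off-schedule vanishes from all the tables, and the documents do not support that. What remains affected is the measured and graded exam data, which enter the adverse-event tables only when recorded as an event.

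A reader might also infer a flat contradiction with SAP 9.3 and Protocol 10.1.2 ("No data will be excluded for any reason"). That sentence sits in a population definition and can fairly be read as governing what belongs to the analysis set, not which visits fill a table. Unscheduled readings stay in the data and the listings. The two rules are in tension, no more.

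Nor are early-exit readings lost: "Information from Early Exit Visits should be recorded on the Visit 6/Exit Visit pages".

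Leaving off-schedule readings out of by-visit tables is ordinary practice, and for three of the four exams the protocol promises nothing else. That also stands. It does not answer the IOP point. The protocol's IOP sentence does open with by-visit summaries, but it then attaches an any-time qualifier to the 30 mm Hg threshold, and the SAP drops that qualifier.

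**Conclusion.** The point holds in limited form. Under SAP 6.4, with no exception in SAP 15.2 to 15.5, objective safety readings from unscheduled visits are confined to listings. The any-time IOP ≥30 mm Hg proportion specified in the protocol is replaced by a per-visit one, and SAP 17 does not say so. That is an undeclared departure in a safety summary. It can only lower the number of patients shown as ever reaching the threshold.

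The size is unknown. Each affected patient is 2.9 percentage points in an arm of 35, provided that patient has no reading of ≥30 mm Hg at a scheduled visit. A reader might infer that the comparison between arms is biased toward no difference. That would require more off-schedule findings in one arm than another, which the documents neither predict nor rule out.

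For acuity, slit lamp and ophthalmoscopy the gap is one of completeness. It does not depart from the protocol.

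**What to change.** 1. In SAP 6.4, limit the exclusion to efficacy tables and by-visit tables.
2. In SAP 15.5, restore the per-patient proportion with IOP ≥30 mm Hg at any time after the first dose, using scheduled and unscheduled readings. Give the ≥10 mm Hg rise from baseline on the same basis. Keep the by-visit rows.
3. In SAP 15.2 to 15.4, add one per-patient worst post-dose summary by arm for acuity change, slit lamp and ophthalmoscopy, from the same readings. This goes beyond the protocol but closes the same gap. Early-exit readings need no special rule.
4. Add these summaries to the table list in SAP 20. If the sponsor prefers to keep IOP ≥30 mm Hg per visit only, declare that in SAP 17.

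The cost is SAP wording and a few derivations. The readings are already in the eCRF, so no new data are collected. The downside is that the reported safety rates may look slightly less favourable. Patients examined more often also have more chances to show an abnormality, so the number with any unscheduled exam should be shown by arm beside these summaries.
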